**Study protocol and statistical analysis plan**

**Thessaloniki, 5 October 2017**

## Study protocol and statistical analysis plan

This was a prospective observational cohort study with unselected, consecutive septic patients being included. Thirty-two adult septic patients hospitalized in a general intensive care unit were studied during the first 24h of treatment and after the discharge from the ICU setting. The unit has a capacity of 15 beds and is located in a large tertiary hospital in northern Greece. The study was conducted from March to August 2017. The protocol had the approval of the ethics committee of the hospital. Subjects were included if they developed sepsis plus AKI during their hospitalization in the ICU, regardless of the underlying cause. The presence of Acute Kidney Injury was determined according to the KDIGO guidelines, i.e. at least stage 1 AKI. The categorization of AKI as transient or persistent was determined by the normalization of the kidney function after the administration of appropriate therapy and support in the ICU environment and after 3 days of hospitalization. For the purpose of the study all consecutive patients suffering from sepsis were included, with the exception of those surviving less than three days, in order to determine whether they had AKI (persistent or not).

After the determination of sepsis, patients were divided into 3 distinct groups: Group 1 included the patients without progression to AKI, Group 2 included the patients with transient AKI and Group 3 comprised of the patients with persistent kidney injury. For every group a series of functional physiological parameters were recorded or measured: Age, sex, mortality, hospitalization days in ICU, baseline Urea and Creatinine, SOFA and APACHE II scores upon admission to ICU, Lactates, Urine Urea and Creatinine, Fractional Excretion of Sodium (FENa), the Urine Urea to Plasma Urea and the Urine Urea to Plasma Creatinine ratio, the Urine Potassium to Urine Sodium ratio, Plasma urea/creatinine ratio, the Daily Diuresis and the Fluids Balance during the first 3 days of ICU stay and the Hematocrit. Other parameters recorded were related to the cardiac function as assessed by the heart ultrasound [Velocity-Time Integral calculated at the aortic valve (VTI) and the Cardiac Index (CI)], as well as respiratory parameters in mechanically ventilated patients (Respiratory Compliance, Tidal Volume - Vt, Oxygen Saturation of Hemoglobin – SaO2, PaO2 to FiO2 ratio) or circulatory system indexes, like Mean Arterial Pressure (MAP), heart rate (HR) and dosage of vasoactive agents.

The US examinations were performed by three ICU medical doctors under the supervision of a senior consultant, experienced in abdomen US. A standard convex transducer for abdominal exploration was used for the identification of renal vasculature and the calculation of the resistive index. B-mode US in the posterior-lateral approach allowed localization of the kidneys and evaluation of renal parenchyma. In all patients, simultaneous recordings of color Doppler ultrasound for semi-quantitative evaluation of renal vasculature and pulse Doppler ultrasound for the calculation of RI were performed. The former led to a grading from 0 (no identifiable renal vasculature) to 3 (fully identifiable renal vessels up to the arcuate arteries) (Table 1). The Resistive Index is calculated employing the following formula: RI=

[peak systolic velocity - minimum diastolic velocity] / peak systolic velocity. Assessment of both kidneys was performed and at least three values for RI were obtained from each kidney. The average value from all the measurements was considered the final value for every case.

Table 1: Color-Doppler for a semi-quantitative evaluation of intra-renal vascularization

Stage	Quality of renal perfusion by color-Doppler
0	Unidentifiable vessels
1	Few vessels visible near the hilum
2	Hilar and interlobar vessels in most of the renal parenchyma
3	Renal vessels identifiable until the arcuate arteries in the field of view

#### Statistics

The study parameters were tested for compliance with the normal distribution with the Kolmogorov-Smirnoff test. For the comparison between the 3 groups of patients the one-way Analysis of Variance (ANOVA) was utilized. The Bonferroni post-hoc analysis was employed to reveal statistical differences in means between the three groups of patients. For discrete variables, the  $\chi^2$  test was used. Correlations between various parameters were explored using the Pearson's correlation test. The identification of independent variables predicting persistent AKI was based on multivariate logistic regression analysis. Finally, the creation of the ROC curve for the calculated RI values was used to determine the ideal cut-off value of the RI concerning the prediction of persistent AKI in this pool of participants, rendering the respective sensitivity and specificity characteristics.

Statistical significance level was set to 0.05. All statistical analyses were performed using the SPSS v.15 (IBM) statistical software.

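### The Statistics section offers only an order-blind chi-square for discrete variables; if the 0-3 colour-Doppler grade is compared across the AKI groups that way, a large directional shift is easier to miss (minor)

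*Combined protocol and SAP*

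**What the plan says.** The study protocol section reports that "Thirty-two adult septic patients hospitalized in a general intensive care unit were studied" and divides them into three groups: no AKI, transient AKI and persistent AKI. Group sizes are not given.

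The grade belongs to the ultrasound protocol: "In all patients, simultaneous recordings of color Doppler ultrasound for semi-quantitative evaluation of renal vasculature" were made alongside the pulse Doppler used for RI. Table 1 sets out four ordered levels, from no vessel that can be identified up to "Renal vessels identifiable until the arcuate arteries in the field of view".

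The Statistics section does not mention the grade. For group comparisons it offers two tools: one-way ANOVA with a Bonferroni follow-up, and a chi-square test. The junction between them reads "statistical differences in means between the three groups of patients. For discrete variables, the", with chi-square named next. Pearson correlation, logistic regression and a ROC curve for RI complete the list. No method for ordinal data is named.

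**The concern.** A four-level grade can reasonably be taken as a discrete variable, and the only rule for those is chi-square. Pearson's chi-square gives the same answer whichever way the grade columns are shuffled. It spreads its sensitivity over 6 degrees of freedom instead of concentrating it on a move up or down the scale.

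The clinically interpretable pattern here would be such a move: perfusion grade falling, or rising, from no AKI to persistent AKI. If chi-square was used and a large shift of that kind exists, the comparison is more likely to be reported as non-significant than it would be with a rank test. What is at stake is a missed difference in a supporting ultrasound measure, not a false positive.

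**Working it through.** The plan states no power or effect size, so there is no figure of its own to reproduce.

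**Inputs from the documents.** N = 32; 3 groups; 4 ordered grades; significance level 0.05.

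**Assumptions.** Group sizes, grade distributions and effect sizes. None of these is in the documents.

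**Step 1: sparsity.** A 3 x 4 table has 12 cells, so the mean expected count is 32/12 = 2.7. Over all possible margins with N = 32, at most 4 of 12 cells (four grades seen) or 5 of 9 (three grades seen) can have an expected count of 5 or more. Hence the preference for an exact or permutation p-value.

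**Step 2: one assumed table.** Counts for grades 0/1/2/3:

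| Group | 0 | 1 | 2 | 3 | n |
|---|---|---|---|---|---|
| 1 | 1 | 1 | 4 | 5 | 11 |
| 2 | 1 | 3 | 4 | 3 | 11 |
| 3 | 4 | 3 | 2 | 1 | 10 |
| Total | 6 | 7 | 10 | 9 | 32 |

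- *Chi-square.* Each expected count is row total x column total / 32, e.g. 10 x 6/32 = 1.875 for Group 3, grade 0. Summing (O - E)²/E by row gives 2.64 + 0.79 + 4.28 = 7.71 on (3 - 1)(4 - 1) = 6 df, p = 0.26. Shuffling the columns leaves this unchanged.
- *Kruskal-Wallis.* Mid-ranks for grades 0 to 3 are 3.5, 10, 18.5 and 28. Rank sums are 227.5, 191.5 and 109.
 - Uncorrected H = 12/(32 x 33) x (227.5²/11 + 191.5²/11 + 109²/10) - 3 x 33 = 5.853.
 - Tie correction = 1 - (210 + 336 + 990 + 720)/(32³ - 32) = 0.931.
 - H = 5.853/0.931 = 6.29 on 2 df; p = exp(-6.29/2) = 0.043.

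The same 32 assumed patients fall on opposite sides of 0.05.

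**Step 3: power by simulation.** Proportional-odds shifts with 4000 runs per scenario.

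- Splits (Groups 1/2/3): 11/11/10, 16/8/8, 22/5/5, 8/16/8, 8/8/16, 5/5/22.
- Group 1 grade distributions: 25/25/25/25, 10/30/40/20 and 5/15/35/45%.
- Log-odds shifts for Groups 2/3: 0.35/0.7, 0.75/1.5 and 1.25/2.5, up and down. Group 3 versus 1 odds ratios are exp(0.7) = 2.0, exp(1.5) = 4.5 and exp(2.5) = 12.2.
- Scenarios per effect: 6 x 3 x 2 = 36.

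To show how large 12.2 is: with Group 1 at 10/30/40/20% and a downward shift, the odds of grade 0 go from 0.1/0.9 = 0.111 to 0.111 x 12.18 = 1.35, so 57% of Group 3 would be at grade 0 against 10% of Group 1.

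| Odds ratio, Group 3 vs 1 | Chi-square power | Permutation Kruskal-Wallis power | Gain in points (median) | Gain, both tests by permutation |
|---|---|---|---|---|
| 2 | under 13% | under 13% | -1 to +6 (about 3.5) | 0 to +5 |
| 4.5 | 4-32% | 18-36% | +1 to +18 (13) | +3 to +16 |
| 12.2 | 8-66% | 38-78% | 0 to +34 (about 21) | +6 to +33 |

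At 12.2 with Group 1 at 10/30/40/20%, a downward shift and asymptotic p-values for both tests, power was 51% (chi-square) versus 74% (Kruskal-Wallis) for 11/11/10, 50% versus 76% for 16/8/8, and 61% versus 68% for 5/5/22. The smallest gains at 4.5 and 12.2 occurred at 5/5/22.

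**Step 4: checks.**

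- With no shift, chi-square rejects in 3.2-5.2% of runs and permutation Kruskal-Wallis in 4.2-5.9%, so neither materially exceeds 5%.
- ANOVA on scores 0-3 is within -9 to +6 points of asymptotic Kruskal-Wallis.
- A separate simulation used odds ratios of 2 to 6 per group step and other splits. It put chi-square about 7 to 23 points below Kruskal-Wallis in every shifted scenario.
- Reverse case, spread only: with grades 10/40/40/10% in Groups 1 and 2 and 40/10/10/40% in Group 3, chi-square has 52-74% power and permutation Kruskal-Wallis 1-12%. In a milder version the figures are 15-23% and 2-11%.

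**The case against.** The strongest reply is that the plan never says the grade is compared across groups at all. It is absent from the Statistics section and from the list of parameters recorded for each group. RI is missing from that list too, so the omission suggests rather than proves that no comparison was intended. A reader might infer that chi-square was in fact applied to the grade. The documents do not show that, and the point has to stay conditional.

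Nor is chi-square the only reading. The section introduces ANOVA for comparing the three groups without restriction. Discrete may have meant categorical items such as sex and mortality; taken literally it would also send SOFA and APACHE II scores to chi-square, which is implausible. A grade numbered 0 to 3 and described as semi-quantitative could well have been scored in ANOVA, and then most or all of the loss disappears. This stands, and it lowers the importance of the point.

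The power figures are all assumed, which also stands. At an odds ratio of 4.5 the rank test still reaches only 18-36%, so with 32 patients the sample size is the main limit for anything but a very large shift.

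It can also be argued that Kruskal-Wallis is not the best choice, because it ignores the order of the groups. A linear-by-linear trend test gained a further 5 to 12 points at an odds ratio of 4.5 and 5 to 15 at 12.2, and gives p = 0.014 on the assumed table. That is fair if the groups are declared ordered. The plan does not declare this, so Kruskal-Wallis is the less committal choice. The argument bears on which order-respecting test to use, not on whether chi-square is a good one.

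**Conclusion.** The point holds as a minor improvement. The plan has no ordinal method, and its only rule for discrete variables ignores order. If that rule was used for the grade, the illustrative loss is about 10 to 30 points of power at a Group 3 versus Group 1 odds ratio near 12, less when the split is very unbalanced (5/5/22 among those tried), and little at an odds ratio of 2. If the grade was scored in ANOVA there is largely no loss. All sizes rest on assumed splits, distributions and proportional-odds shifts. The direction holds for large directional shifts and reverses for pure spread differences.

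Two stronger inferences are not supported. Type I error is not inflated. The study's named diagnostic analysis is not compromised either: the ROC curve uses RI alone, and no endpoint is tied to the grade. How two kidneys' grades become one, and what follows from a failed normality test, are separate matters and form no part of this point.

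**What to change.** Add to the Statistics section that, where the colour-Doppler grade is compared across the three groups:

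- the test is Kruskal-Wallis on one grade per patient, with an exact or permutation p-value;
- pairwise comparisons use rank tests with Bonferroni adjustment;
- correlations involving the grade use Spearman instead of Pearson;
- the full group-by-grade table is shown, so that a change in spread stays visible.

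If chi-square has already been run on the grade, report it beside the rank test.

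The cost is a few sentences and a rerun on data already held, with no new measurements. "The study was conducted from March to August 2017", and the plan is dated 5 October 2017 and written in the past tense, so the rank analysis must be labelled post hoc and counted as an added comparison. The statistical price is weaker detection of a pure difference in spread, which is why the full table belongs in the report.

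### The RI cut-off is chosen and scored in the same patients (at most 32), with no stated selection rule, confidence interval or optimism correction

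*Combined protocol and SAP*

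**What the plan says.** The Statistics section takes from the ROC curve the "ideal cut-off value of the RI concerning the prediction of persistent AKI in this pool of participants, rendering the respective sensitivity and specificity" that belong to it. It names no criterion for the best cut-off, no threshold fixed in advance, no resampling or validation, and no interval for the AUC, the cut-off, the sensitivity or the specificity.

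The section headed Study protocol and statistical analysis plan gives the size of the single cohort: "Thirty-two adult septic patients hospitalized in a general intensive care unit were studied". It also gives the timing: "The study was conducted from March to August 2017". The document is dated 5 October 2017.

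The cases are clear: "Group 3 comprised of the patients with persistent kidney injury". The non-cases are not. One sentence says that "all consecutive patients suffering from sepsis were included, with the exception of those surviving less than three days", and a later one says "After the determination of sepsis, patients were divided into 3 distinct groups", the first of which had no AKI. Another sentence in the same section makes AKI in addition to sepsis a condition of inclusion, which would leave the no-AKI group empty.

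**The concern.** A cut-off picked because it separates these patients well has fitted part of their chance variation. Scoring it in the same patients counts that chance variation as accuracy. The smaller the sample, the larger this effect and the wider the uncertainty around each proportion.

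The cut-off is offered for prediction of persistent AKI. With no interval and no correction, a reader cannot tell how much of the reported sensitivity and specificity reflects the RI and how much reflects the search for a threshold. With no stated rule or non-case class, the reader also cannot reproduce the result or say which patients it describes.

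**Working it through.** **No plan figure to reproduce.** The documents give no group sizes, target AUC, expected accuracy or sample-size calculation. The size of the effect therefore has to be shown over a range of assumptions.

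**Inputs**
- From the documents: 32 patients in total, one cohort, one averaged RI value per patient, cut-off and accuracy from the same data.
- Assumed: 8 to 16 cases among 32, or 10 cases v 12 non-cases if only patients with AKI enter; true AUC 0.5 to 0.9; RI normal with equal variances, unrounded, and tending higher in cases; cut-off by Youden or closest to the corner.

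**Formulas** (RI in within-group SD units, non-case mean 0, case mean δ)
- δ = √2 × Φ⁻¹(AUC). For AUC 0.80, δ = 1.19.
- Apparent sensitivity at c: share of observed cases above c. Apparent specificity: share of observed non-cases at or below c.
- True sensitivity at c: 1 − Φ(c − δ). True specificity: Φ(c).
- Youden maximises sensitivity + specificity. The corner rule minimises (1 − sensitivity)² + (1 − specificity)².
- Overstatement: mean of (apparent sum − true sum) over simulated datasets.

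**Result 1: mean overstatement of sensitivity + specificity, Youden, 10,000 datasets per setting**

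| Cases / non-cases | AUC 0.5 | AUC 0.7 | AUC 0.8 | AUC 0.9 |
|---|---|---|---|---|
| 8 / 24 | 0.225 | 0.201 | 0.179 | 0.152 |
| 10 / 22 | 0.211 | 0.186 | 0.168 | 0.141 |
| 12 / 20 | 0.201 | 0.178 | 0.158 | 0.133 |
| 16 / 16 | 0.193 | 0.168 | 0.151 | 0.127 |
| 10 / 12 (AKI only) | 0.231 | 0.206 | 0.184 | 0.156 |

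The corner rule at N = 32 gives about 0.11 to 0.18. At 10 v 12, the range over both rules is about 0.13 to 0.23. The AUC 0.5 column is pure selection: the RI carries no information, yet the apparent sum still exceeds chance by about 0.2.

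Unequal variances (case SD 0.67 or 1.5 times the non-case SD) change little: 0.12 to 0.21 (Youden) and 0.10 to 0.18 (corner). Rounding RI to 0.2 SD lowers the range to 0.10 to 0.20 and 0.08 to 0.14. The direction held in every setting.

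**Result 2: each measure separately, 11 cases v 21 non-cases, AUC 0.80**

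| Rule | Sensitivity, apparent v true | Specificity, apparent v true | Datasets where the apparent sum does not exceed the true sum |
|---|---|---|---|
| Youden | 0.79 v 0.68 (excess 0.11) | 0.78 v 0.73 (excess 0.05) | 12% |
| Corner | 0.78 v 0.70 (excess 0.08) | 0.78 v 0.73 (excess 0.04 to 0.05 before rounding) | 19% |

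**Result 3: precision.** Exact (Clopper-Pearson) limits for x of n are the 2.5% quantile of Beta(x, n − x + 1) and the 97.5% quantile of Beta(x + 1, n − x). The counts are illustrative.
- 9 of 11 (82%): Beta(9, 3) and Beta(10, 2) give 48% to 98%, a width of 50 points.
- 17 of 21 (81%): Beta(17, 5) and Beta(18, 4) give 58% to 95%, a width of 37 points.

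**Result 4: how much a bootstrap recovers** (11 v 21, AUC 0.80, sensitivity + specificity − 1)
- Youden: apparent 0.578, corrected 0.478, true 0.408. Share of bias removed: (0.578 − 0.478) / (0.578 − 0.408) = 0.100 / 0.170 = 59%.
- Corner: 0.556, 0.474, 0.426. Share: 0.082 / 0.130 = 63%.
- With RI rounded to 0.2 SD, the shares are 62% (Youden) and 80% (corner).

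**The case against.** **The scope is already limited.** The plan confines the cut-off to its own participants, describes an observational cohort, and claims neither a validated threshold nor its use in care. A reader might infer that a validated clinical threshold is being put forward; the documents do not say that. This limits the harm, but it supplies neither an interval nor a correction.

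**The bias is conditional and its size is assumed.** Both are true. If the rule were, say, a fixed sensitivity, these amounts would not apply. A reader might infer that the published accuracy is certainly inflated, or inflated by a known amount. The documents give no rule, group sizes or RI distribution to support that, and in 12% to 19% of datasets in the example the apparent sum was not above the true one. What needs no assumption is the omission of the rule and the intervals.

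**Imprecision matters more than optimism.** This stands. In the example the excess per measure is at most 0.11, against exact intervals 37 to 50 points wide. Exact intervals at the selected cut-off also covered the true value in 92% to 99% of simulated datasets, so plain intervals convey most of the uncertainty.

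**The comparator.** It is tempting to read the contrast as Group 3 v Groups 1 and 2, since three groups are described and all consecutive septic patients are said to be included. The sentence requiring AKI for inclusion points instead to Group 3 v Group 2. The documents do not settle this, and the bias arises under either reading.

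**Conclusion.** The point holds. The plan selects the RI cut-off and reports its accuracy in the same patients, at most 32, with no interval, no correction, no defined rule and an unclear non-case class. Under either usual rule, sensitivity plus specificity is overstated in expectation by roughly 0.1 to 0.2 (about 0.13 to 0.23 at an assumed 10 v 12), given normal, unrounded RI and a true AUC of 0.5 to 0.9. Confidence is high for the omissions and for the direction under those rules, and lower for the exact amounts.

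Nothing here shows that the RI fails to predict persistent AKI. Nor do the documents show that the rule was chosen after seeing the data: the plan is dated after the study period and states no rule, which leaves the question open. This should be fixed, because a better analysis is available at little cost on data already held.

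**What to change.** Amend the Statistics section as follows.

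1. Report the AUC with a 95% confidence interval.
2. Report sensitivity and specificity at the selected cut-off, labelled as apparent, with exact 95% intervals.
3. Add bootstrap optimism-corrected values: at least 1000 resamples within cases and non-cases, re-selecting the cut-off by the same rule each time, with a bootstrap 95% interval for the cut-off. Note that this removes only part of the bias at this sample size.
4. Reconcile the conflicting inclusion sentences. State which non-case class and which cut-off rule were actually used, with the number in each class. Report the other contrast as a sensitivity analysis if those patients are available. Label as post hoc any rule not fixed before data collection began in March 2017.
5. Describe the cut-off as hypothesis-generating until it is tested in new patients.

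**Cost.** A few sentences and a short script on held data, possibly outside SPSS v.15. The reported accuracy will look less favourable, and a rule written now must be shown as post hoc. If the bootstrap is not run, items 1, 2, 4 and 5 are the minimum.
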